### 7.1.1 Screening

After signing the study ICF, the screening assessments will be done within 1 to 28 days prior to randomization or within 1 to 7 days prior to randomization for selected assessments (see [Table 7-1a](#) for the list of assessments to be performed).

**Note:** Any screening assessment that is done outside the screening window (Day -28 to Day -1 or Day -7 to Day -1 as applicable) must be repeated prior to randomization.

Re-screening of patients is only allowed once per patient if the patient was not registered as entering the treatment phase before (i.e. IRT randomization). In this case the Subject No. assigned to the patient initially will be used and the patient will be identified with this number throughout her entire participation to the study.

Any screening assessments required within -7 to -1 days must be repeated if Cycle 1 Day 1 visit is delayed more than 7 days after randomization visit. For laboratory evaluations used to determine eligibility, a repeated evaluation within the screening window is permitted for screening results out of the defined range. If the repeated laboratory result meets the criteria, that result may be used to determine eligibility. If the repeated laboratory result does not meet the criteria, the patient will be considered a screening failure. In case rescreening occurs, all evaluations re-assessed should meet the eligibility criteria. A new informed consent form must be signed only if there is an interruption in the patient's eligibility evaluation and the investigator chooses to re-screen the patient following screen failure; the 28 day screen period does not apply to the informed consent process. If a new informed consent form is signed, adverse events and medical history will be assessed relative to the new informed consent date.

Assessments of patient reported outcomes should be collected prior to any clinical assessments, drug dosing or diagnostic testing.

[figure not shown]
Any imaging assessments already completed during the regular work-up of the patient within 28 days prior to randomization, including before signing the main study ICF can be considered as the baseline images for this study.

#### 7.1.1.1 Eligibility screening

Following registering in the IRT for screening, patient eligibility will be checked once all screening procedures are completed. The eligibility check will be embedded in the IRT system. Please refer and comply with detailed guidelines in the IRT manual.

#### 7.1.1.2 Information to be collected on screening failures

Patients who sign an informed consent but fail to be started on treatment for any reason will be considered a screen failure. The reason for not being started on treatment will be entered on the Screening Phase Disposition Page. The demographic information, informed consent, and Inclusion/Exclusion pages must also be completed for Screen Failure patients. No other data will be entered into the clinical database for patients who are screen failures, unless the patient experienced a Serious Adverse Event during the Screening Phase (see [Section 8.2](#) for SAE reporting details).

### **7.1.1.3 Patient demographics and other baseline characteristics**

The data that will be collected on patient characteristics at screening includes:

- Demography (Date of birth and initials (where permitted), sex, race, ethnicity, source of patient referral)
- Diagnosis and extent of cancer (including staging at study entry and histology/cytology)
- Medical history (e.g., important medical, surgical, and allergic conditions from the patient's medical history which could have an impact on the patient's evaluation) / current medical conditions (e.g., all relevant current medical conditions which are present at the time of signing informed consent). Ongoing medical conditions, symptoms and disease which are recorded on the Medical History eCRF should include the toxicity grade.
- ER, PgR and HER2 status
- All prior antineoplastic therapies including surgical interventions and chemo-, biologic-, immunologic- and radiation-therapies provided as treatment for cancer prior to the administration of study drug.
- All medications and significant non-drug therapies taken within 30 days before the first dose is administered. They must be recorded on the Prior and Concomitant medication or Surgical and medical procedures eCRF page and updated on a continual basis if there are any new changes to the medications.
- Patient-reported outcome questionnaires (EORTC QLQ-C30, EQ-5D-5L, and BPI-SF (See [Section 7.2.6](#))).

Furthermore the following assessments will be performed:

- Vital signs
- Height, weight
- Physical examination
- Performance status (ECOG)
- Laboratory evaluations (hematology, PT, INR, chemistry, lipid panel, urinalysis)
- ECG
- ECHO/MUGA
- Radiological assessments (e.g. CT Scan)

### **7.1.2 Treatment period**

Patients will be treated with fulvestrant + ribociclib or fulvestrant + placebo until disease progression, unacceptable toxicity, withdrawal of consent by the patient, patient is lost to follow up, death, discontinuation from the study treatment due to any other reason or the sponsor terminates the study. For details of assessments, refer to [Table 7-1a](#) and [Table 7-1b](#).

### **7.1.3 Discontinuation of Study Treatment**

Patients may voluntarily discontinue from the study treatment for any reason at any time. If a patient decides to discontinue from the study treatment, the investigator must make a reasonable effort (e.g. telephone, e-mail, letter) to understand the primary reason for this decision and record this information in the patient's chart and on the appropriate CRF pages. They may be

considered withdrawn if they state an intention to withdraw, fail to return for visits, or become lost to follow-up for any other reason.

The investigator should discontinue study treatment for a given patient if, he/she believes that continuation would be detrimental to the patient's well-being. Patients may voluntarily withdraw from the study or be dropped from it at the discretion of the investigator at any time.

Patient may be withdrawn from the study treatment under the following circumstances:

Emergence of adverse events where the recommendation as per [Section 6.5.1.2](#) is discontinuation of ribociclib therapy (including, but not limited to QTcF  $\geq$  501 msec, confirmed at repeated ECG measurements and recurrent after dose adjustment was performed; documented episode of ventricular tachycardia, or ventricular fibrillation; complete heart block (Grade III AV block) or Second degree AV block Mobitz type II as well as any relevant hepatotoxicity events).

- Lost to follow up
- Physician decision
- Progression of disease
- Study terminated by the sponsor
- Protocol deviation
- Technical problems.

Patient must be withdrawn from the study treatment if any of the following occur:

- Pregnancy
- Death
- Subject/guardian decision

In addition to the general withdrawal criteria, the following study specific criteria will also require study treatment discontinuation:

- Adjustments to study treatment due to toxicity that result in discontinuation. Please refer to [Section 6.5](#)
- Use of prohibited medication. Please refer to [Section 6.6.3](#)
- Any other protocol deviation that results in a significant risk to the patient's safety.

The appropriate personnel from the site and Novartis will assess whether study treatment should be discontinued for any patient whose treatment code has been broken inadvertently for any reason.

Patients who discontinue study treatment should NOT be considered withdrawn from the study. They should return for the assessments indicated in [Section 7.1.5](#) and [Section 7.1.6](#). If they fail to return for these assessments for unknown reasons, every effort (e.g. telephone, email, letter) should be made to contact them as specified in [Section 7.1.7](#). The patient remains on study until such time as he/she completes protocol criteria for ending study assessments. At that time, the reason for study completion should be recorded on the End of Post Treatment Phase Disposition CRF page.

Patients who discontinue study treatment should be scheduled for an End of Treatment (EOT) visit within 15 days following the date study treatment is permanently discontinued, at which

time all of the assessments listed for the EOT visit will be performed. For details of assessments, refer to [Table 7-1](#). If the decision to discontinue the patient occurs at a regularly scheduled visit, that visit may become the EOT visit rather than having the patient return for an additional visit.

An End of phase disposition eCRF page should be completed, giving the date and reason for stopping the study treatment. If a withdrawal occurs, or if the patient fails to return for visits, the investigator must determine the primary reason for a patient's premature withdrawal from the study and record this information on the EOT eCRF page. The EOT visit is not considered the end of the study.

At a minimum, all patients who discontinue study treatment, including those who refuse to return for a final visit, will be contacted for safety evaluations during the 30 days following the last dose of study treatment.

The investigator must also contact the IRT to register the patient's discontinuation from study treatment.

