#### **6.5.1.2 Ribociclib/placebo**

Recommendations for dose reduction, interruption or discontinuation of ribociclib in the management of study drug related adverse reactions are summarized in [Table 6-4](#), [Table 6-5](#), [Table 6-6](#), [Table 6-7](#) and [Table 6-8](#). No dose modification for fulvestrant is permitted.

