**Table 6-3 Dose modification guidelines**

	Ribociclib/placebo ( 3 weeks on/1 week off schedule)		Fulvestrant	
	Dose	Number of capsules & strength	Dose	Number of injections & strength
Starting dose	600 mg	3 x 200 mg capsules	500 mg	2 x 250mg (5 mL) injections
First dose reduction	400 mg	2 x 200 mg capsules	No dose modification allowed	
Second dose reduction	200 mg	1 x 200 mg capsules	No dose modification allowed	

Clinical judgment of the treating physician should guide the management plan of each patient based on individual benefit/risk assessment. However, for events requiring a discontinuation in [Table 6-4](#), [Table 6-5](#), [Table 6-6](#), [Table 6-7](#) and [Table 6-8](#) or listed in [Section 7.1.3](#), treatment must be discontinued.

Unscheduled local laboratory assessments may be performed if medically indicated to document a (potential) adverse event or when the treating physician cannot wait for central laboratory results for decision making (e.g. dose modifications). In this particular situation, if possible, the blood sample obtained at the same time point should be submitted to the central laboratory for analysis in parallel with local analysis.

The results of the local laboratory will be recorded in the eCRF if any of the following criteria are met:

[figure not shown]
- A treatment decision was made based on the local results, or
- Local lab results document an adverse event not reported by the central lab, or
- Local lab results document an adverse event severity is worse than the one reported by the central lab, or
- There are no concomitant central results available.

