
3 QTcF <math>\geq 501</math> ms on at least two separate ECGs
	
Interrupt ribociclib/placebo. Perform steps 1-4 as directed in “For All Grades.” Perform a repeat ECG within one hour of the first QTcF of <math>\geq 501</math> ms. If QTcF remains <math>\geq 501</math> ms, consult with a cardiologist (or qualified specialist) and repeat cardiac monitoring as indicated until the QTcF returns to <math>< 481</math> ms.  
 
If QTcF returns to <math>< 481</math> ms, ribociclib/placebo will be reduced by 1 dose level. Refer to Table 6-3 for dosing schedule.
 
If QTcF remains <math>\geq 481</math> ms after performing steps 1-4 as directed in “For All Grades” discontinue ribociclib/placebo.
 
 Repeat ECGs 7 days and 14 days after dose resumption (then as clinically indicated) for any patients who had therapy interrupted due to QTcF <math>\geq 501</math> ms. If QTcF of <math>\geq 501</math> ms recurs, discontinue ribociclib/placebo

4* [QT/QTcF <math>\geq 501</math> or <math>> 60</math> ms change from baseline] and [Torsades de pointes or polymorphic ventricular tachycardia, or signs/symptoms of serious arrhythmia]
	
Discontinue ribociclib/placebo. Perform steps 1-4 as directed in “For All Grades.”  
 
Obtain local cardiologist (or qualified specialist) consultation and repeat cardiac monitoring as indicated until the QTcF returns to <math><481</math> ms.
 

*All values refer to the average of triplicate measurements
	

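### Protocol 7.1.3 lists cardiac and hepatic stopping events as optional although 6.5.1.2 makes them mandatory, the dose tables can point to a restart for some of them, and 7.2.2.6.1 names the wrong agent to hold

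*Protocol*

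**What the plan says.** Four parts of the protocol bear on this.

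- **Section 6.5.1.2.** The text below Table 6-3 begins "However, for events requiring a discontinuation in" Tables 6-4 to 6-8, extends the rule to events listed in Section 7.1.3, and ends "treatment must be discontinued". The same section says of the partner drug: "No dose modification for fulvestrant is permitted".
- **Section 7.1.3.** The first list opens "Patient may be withdrawn from the study treatment under the following circumstances". Its first item is adverse events for which 6.5.1.2 recommends stopping ribociclib. The examples are recurrent QTcF of at least 501 ms, ventricular tachycardia or fibrillation, and "complete heart block (Grade III AV block) or Second degree AV block Mobitz type II as well as any relevant hepatotoxicity events". A second list, of cases where the patient *must* be withdrawn, holds only pregnancy, death and subject/guardian decision. Further down, "the following study specific criteria will also require study treatment discontinuation", and the first bullet there is "Adjustments to study treatment due to toxicity that result in discontinuation. Please refer to" Section 6.5.
- **Dose tables.** The grade 4 row of Table 6-6 stops ribociclib/placebo for "Torsades de pointes or polymorphic ventricular tachycardia, or signs/symptoms of serious arrhythmia", but only together with a QT/QTcF of at least 501 ms or a change from baseline above 60 ms. Section 6.5.1.2.3 sends all other adverse events to Table 6-8.
- **Section 7.2.2.6.1.** At QTcF of 481 ms or more after randomization, it requires study treatment to be interrupted and refers to Table 6-6. Section 6.1 defines study treatment as the combination, fulvestrant included.

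**The concern.** These are stop and hold rules for a drug that prolongs the QT interval. They apply to patients still taking ribociclib and to placebo patients who first receive it at cross-over under Amendment 4.

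A site deciding whether to stop will open the section on discontinuation. There it finds the toxicity item in the same list as physician decision and technical problems, with a stricter list directly below that omits it. If the site then turns to the dose tables for heart block, it finds no row for the event and falls through to general by-grade rules that can lead to a restart.

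The second issue is which drug is affected. Read literally, the ECG section would also hold fulvestrant, although the rest of the protocol keeps fulvestrant going.

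**Working it through.** No arithmetic applies. The check sets the rules side by side.

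**1. May or must.** Section 6.5.1.2 says the 7.1.3 events must lead to discontinuation. Section 7.1.3 says they may. Its later line on toxicity says discontinuation is required. Two of the three statements point to a mandatory stop for ribociclib, so that is the better reading. The *may* heading remains out of step with the other two, and the *must* list does not contain the events.

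**2. What the dose tables do with each event named in 7.1.3.**

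- Recurrent QTcF of at least 501 ms: the grade 3 row of Table 6-6 stops ribociclib/placebo.
- Hepatotoxicity: Table 6-5 has its own stopping criteria.
- Ventricular tachycardia: Table 6-6 names only the polymorphic form, in the grade 4 row and subject to the QTcF criterion.
- Ventricular fibrillation, complete heart block, Mobitz II: named in no table. Any of them might reach the grade 4 row as a serious arrhythmia, but only if the same QTcF criterion is met.

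Without the QTcF criterion, these arrhythmia and conduction events go to Table 6-8:

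- Grade 1: no dose adjustment.
- Grade 2: interrupt, then restart at the same dose.
- First grade 3: interrupt, then restart one level lower.
- Recurrence at grade 3, or grade 4: stop.

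For the same event, the text of 6.5.1.2 combined with 7.1.3 means a permanent stop, while Table 6-8 means continuing or restarting unless the event is grade 4 or a grade 3 recurrence. The cross-references do not settle it. Section 7.1.3 describes the events as those for which 6.5.1.2 recommends stopping, and for heart block the only specific stop in 6.5.1.2 is its pointer back to 7.1.3.

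**3. Which drug.** At QTcF of 481–500 ms, Table 6-6 interrupts ribociclib/placebo. Section 7.2.2.6.1 interrupts study treatment, which by Section 6.1 is both drugs. Section 6.5.1.2 permits no fulvestrant modification, Section 6.1.1 says there is no rest in the fulvestrant schedule, and Section 6.1.2 lets a patient who stops ribociclib/placebo continue on fulvestrant. The toxicity bullet in 7.1.3 has the same ambiguity.

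**4. Effect on the analyses.** Under Section 3.8.1.1 of the SAP for the primary PFS analysis, stopping study treatment is not a reason for censoring. Protocol Section 10.7.2 makes every analysis after Amendment 4 descriptive. The SAP's summary of partial discontinuation (Section 3.5.5 of the final-CSR version) could be touched slightly, but Section 6.1.2 already leaves continued fulvestrant to the investigator.

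**The case against.** The strongest reply is that 7.1.3 merely enumerates reasons for withdrawal. Its *may* list also contains progression, loss to follow-up and study termination, none of which is at the investigator's option, and Section 14.2.31 of Appendix 2 uses the same form. On that view, the patient may come off the combination where ribociclib has to stop. This agrees with 6.1.2, and the obligation itself sits in 6.5.1.2, which names 7.1.3 expressly. The later toxicity bullet can be read as self-limiting, since it points to Section 6.5, where only ribociclib/placebo is adjusted.

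Much of this stands. A reader might infer that the protocol leaves these stops optional, or that it has no stop rule for heart block. The documents support neither. All the events are mandatory stops through 6.5.1.2, and Table 6-8 itself stops at grade 4 and on recurrence at grade 3. A reader might also infer that sites would restart ribociclib after Mobitz II block. That would require overlooking 6.5.1.2 and would depend on the event being graded 2 or 3, and the documents give no grading for AV block.

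On the ECG section, the pointer to Table 6-6 is in the same sentence as the loose wording. Fulvestrant is also given every 28 days after the first cycle, so a short hold matters only if an injection falls due during it.

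The reply does not remove the separate *must* list that omits these events, the by-grade rules that contradict the mandatory stop, or the naming of both drugs where one is meant.

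**Conclusion.** The protocol is wrong as written: its cardiac and hepatic safety rules are internally inconsistent, to a minor to moderate degree. Section 7.1.3 uses permissive wording for events that 6.5.1.2 makes mandatory stops. For arrhythmia and conduction events outside the QTcF criterion, Table 6-8 can allow a restart that 6.5.1.2 forbids. Section 7.2.2.6.1 names study treatment where ribociclib/placebo is meant.

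The conclusion rests on the current text and on the Section 6.1 definition of study treatment. It assumes no AV-block grade, and no count of affected patients can be derived. It says nothing against the trial's results: PFS, OS, alpha and power are unaffected.

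**What to change.** - In 7.1.3, move the adverse-event item to the *must* list, worded as: ribociclib/placebo must be permanently discontinued; fulvestrant may continue per Section 6.1.2. Reword the study-specific toxicity bullet to match.
- In 7.2.2.6.1, name ribociclib/placebo instead of study treatment as what must be interrupted.
- Add a row or note to Table 6-6 or Table 6-8: ventricular tachycardia or fibrillation, complete heart block and Mobitz II block mean discontinue ribociclib/placebo regardless of grade.

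The cost is a written amendment under Section 12.1, with ethics committee approval and Health Authority approval where required. It needs no new procedures, data or analyses.

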#### **7.1.3.1 Replacement policy**

Not applicable.

#### **7.1.4 Withdrawal of Consent**

Subjects may voluntarily withdraw consent to participate in the study for any reason at any time. Withdrawal of consent occurs only when a subject:

- Does not want to participate in the study anymore, and
- Does not allow further collection of personal data.
  - In this situation, the investigator should make a reasonable effort (e.g. telephone, e-mail, letter) to understand the primary reason for the subject's decision to withdraw his/her consent and record this information. Study treatment must be discontinued and no further assessments conducted, and the data that would have been collected at subsequent visits will be considered missing. Further attempts to contact the subject are not allowed unless safety findings require further communication or follow-up.
  - All efforts should be made to complete the assessments prior to study withdrawal. A final evaluation at the time of the subject's study withdrawal should be made as detailed in the assessment table.

Novartis will continue to keep and use collected study information (including any data resulting from the analysis of a subject's samples until their time of withdrawal) according to applicable law.

For US and Japan: All biological samples not yet analyzed at the time of withdrawal may still be used for further testing/analysis in accordance with the terms of this protocol and of the informed consent form.

For EU and RoW: All biological samples not yet analyzed at the time of withdrawal will no longer be used, unless permitted by applicable law. They will be stored according to applicable legal requirements.

### **7.1.5 Follow up for Safety Evaluations**

All patients will be followed up for safety up to 30 days after last dose of study treatment (fulvestrant + ribociclib/placebo). Patients whose treatment is interrupted or discontinued due to an AE, including abnormal laboratory value, must be followed until resolution or stabilization of the event, whichever comes first. This could include all study assessments appropriate to monitor the event.

Data collected should be added to the Adverse Events CRF and the Concomitant Medications CRF.

### **7.1.6 Efficacy follow-up**

For patients who discontinue treatment for reasons other than disease progression, death, lost to follow-up, or withdrawal of consent, tumor assessments (see [Section 7.2.1.1](#)) and patient reported outcomes (see [Section 7.2.6](#)) must continue to be performed every 8 weeks during the first 18 months, then every 12 weeks until 36 months and thereafter clinically indicated until disease progression, death, lost to follow-up, or any other reasons listed in [Section 7.1.9](#). At that time, the reason for study completion should be recorded on the End of Post treatment phase Disposition eCRF page. If a patient starts a new anti-cancer therapy prior to progression, tumor evaluations should continue with the same above schedule ([Table 7-1a](#) and [Table 7-1b](#)) until disease progression is documented.

